3.3.1.3 Study Periods

For listings of adverse events, lipid levels, laboratory values, vital signs and ECG, values will be allocated to a study period. The allocation to the study periods will be performed after any imputation of missing dates (for AEs only) as described in Section 3.3.1.2. The study periods are defined as follows:

- Pre-treatment: Before first date of study drug (Day <1).
- On-treatment: From Day 1 to date of end of study.

3.3.2 Visit Window

Study visits windows are defined in the table below:

	Screening		Treatment Period							EDV	Follow-up period ^a	Final Follow-up Visit ^b
Visit Number	1	2	3	4	5	6	7	8	9		10, 11, 12, 13, 14, 15	16
Study Week			0	1	3	4	6	8	10		12, 14, 16, 18, 20, 22	24
Study Day	Days -28 to -10	Days -7 to -4	Day 1	Day 8	Day 22	Day 29	Day 43	Day 57	Day 71		Days 85, 99, 113, 127, 141, 155	Day 169
Visit Window				± 1 day	± 2 days		± 2 days	± 2 days				

Analysis Visit Windows

Analysis visit windows will be defined for the lipid parameters, ECG, anti-AZD8233 antibodies, laboratory results and vital signs which summarize values by visit. These analysis visit windows will be exhaustive so that data recorded at any time point has the potential to be summarized. Inclusion within the window will be based on the actual date and not the intended date of visit.

Analysis visit windows will be constructed such that the upper limit of the window intervals fall halfway between two scheduled visits, where the number of days between visits is odd, the additional day will be applied to the lower interval of the later date.

Table 1: Analysis visit windows for lipid parameters, laboratory parameters* and vital signs

Analysis Visits	Scheduled visit day	Analysis visit window (days)
Baseline ^a	Day -28 to Day 1	≤ Day 1
Treatment period		
Day 1	Day 1	Day 1 ^b
Week 1	Day 8	Day 2 – Day 14
Week 3	Day 22	Day 15 – Day 25
Week 4	Day 29	Day 26 – Day 35
Week 6	Day 43	Day 36 – Day 49
Week 8	Day 57	Day 50 – Day 63
Week 10	Day 71	Day 64 – Day 77
Follow-up period		

Week 12	Day 85	Day 78 – Day 91
Week 14	Day 99	Day 92 – Day 105
Week 16	Day 113	Day 106 – Day 119
Week 18	Day 127	Day 120 – Day 133
Week 20	Day 141	Day 134 – Day 147
Week 22	Day 155	Day 148 – Day 161
Week 24	Day 169	Day 162 onwards.

*Complement activation panel is collected pre-dose on Visits 12, 3, 6 and 8 only. Hs-CRP is collected at Visit 1, 8 and all follow-up visits.

^a Baseline is defined as the last measurement prior to first dose of study treatment. Pre-dose values on Day 1 qualify as baseline measurements.

^b Day 1 is defined as date of first dose of study treatment. Includes all measurements collected at Day 1 after the first dose of IP.

Table 2: Analysis visit windows for ECG

Analysis Visits	Scheduled visit day	Analysis visit window (days)
Baseline ^a	Day -28 to Day 1	≤ Day 1
Treatment period		
Day 1	Day 1	Day 1 ^b
Week 1	Day 8	Day 2 – Day 18
Week 4	Day 29	Day 19 – Day 42
Week 8	Day 57	Day 43 – Day 70
Follow-up period		
Week 12	Day 85	Day 71 – Day 91
Week 14	Day 99	Day 92 – Day 112
Week 18	Day 127	Day 113 – Day 140
Week 22	Day 155	Day 141 onwards

^a Baseline is defined as the last measurement prior to first dose of study treatment. Pre-dose values on Day 1 qualify as baseline measurements.

^b Day 1 is defined as date of first dose of study treatment. Includes all measurements collected at Day 1 after the first dose of IP.

Table 3: Analysis visit windows for anti AZD8233 antibodies

Analysis Visits	Scheduled visit day	Analysis visit window (days)
Baseline ^a	Day -28 to Day 1	≤ Day 1
Treatment period		
Day 1	Day 1	Day 1 ^b
Week 1	Day 8	Day 2 – Day 18
Week 4	Day 29	Day 19 – Day 42
Week 8	Day 57	Day 43 – Day 70
Follow-up period		
Week 12	Day 85	Day 71 – Day 98
Week 16	Day 113	Day 99 – Day 126
Week 20	Day 141	Day 127 – Day 154
Week 24	Day 169	Day 155 onwards.

^a Baseline is defined as the last measurement prior to first dose of study treatment. Pre-dose values on Day 1 qualify as baseline measurements.

^b Day 1 is defined as date of first dose of study treatment. Includes all measurements collected at Day 1 after the first dose of IP.

An early discontinuation visit (EDV) may take place at any point during the study up to Week 12. In this instance, follow-up visits (Week 2, Week 4 etc.) will begin at date of last administered treatment and performed every 2 weeks after last dose prior to study discontinuation. For those patients with an early discontinuation, an additional analysis visit window will be applied to follow-up visits as follows and will be used for the summary of safety and lab data.

If there is more than one value per subject within an analysis visit window then the closest value to the scheduled visit date will be summarized, or the later value if the values are equidistant from the nominal visit date, the remaining visits will be treated as ‘Unscheduled Visits’ Listings will display all values contributing to a time point for a subject and will highlight the value that contributed to the summary table where feasible.

For summaries showing the maximum or minimum values, the maximum/minimum value recorded on treatment will be used, regardless of where it falls in an interval. For summaries

at a subject level (i.e., the maximum) all values will be included regardless of whether they appear in a corresponding visit-based summary.

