- a Weight should be measured in light indoor clothes, without shoes, after using the bathroom. Otherwise, follow the local standard procedure.
- b Injection Site Reaction assessments to be collected based on adverse event collection criteria.
- c Vital signs and ECG to be measured pre-dose on dosing days.
- d Blood samples for complement activation panel will be taken around C_{max} and are to be collected pre-dose and 2 hours (± 5 minutes) post-dose.
- e Samples to be obtained pre-dose on dosing days.
- f PK sampling to be performed at Visits 4 (Day 8), 6 (Day 29), 7 (Day 43), 8 (Day 57), 9 (Day 71), 10 (Day 85), 12 (Day 113), 14 (Day 141), and final follow-up visit/EDV. Schedule of sampling for Visit 6 (Day 29), 8 (Day 57) is shown below.
Visit 6 (Day 29): pre-dose, Visit 8 (Day 57): pre-dose.
- g ADA sampling to be performed at Visits 3 (D 1), 4 (D 8), 6 (D 29), 8 (D 57), 10 (D 85), 12 (D 113), 14 (D 141), and final follow-up visit/EDV. ADA samples to be collected pre-dose on all dosing days.
- h If, for any reason, the sample is not drawn pre-dose on Visit 3 (Day 1), it may be taken at any visit until the final follow-up/EDV visit.
- i Check screening labs and inclusion/exclusion criteria.
- j ECG to be performed during the follow-up period at Visits 10 (Day 85), 11 (Day 99), 13 (Day 127), and 15 (Day 155).
- k Pregnancy test: Serum β -human chorionic gonadotropin (β -hCG) will be performed on all the women participants, irrespective of childbearing potential.
- l Pregnancy test (Day 1): Urine pregnancy test using dipstick will be performed before randomization on all the women participants, irrespective of childbearing potential, at a local laboratory.
- m All the women participants should have FSH and LH levels determined, irrespective of childbearing potential.
- n In the case of early discontinuation, follow-up visit will be performed every 2 weeks after last dose.

[Part C]

Randomization should only proceed if all required assessments have been performed and all inclusion/exclusion criteria as well as other protocol restrictions have been evaluated; see Sections [5](#) and [6.5](#).

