Antidrug Antibodies	There is a potential risk for antibody formation. Emergence of ADA has been observed in a proportion of clinical study participants after repeated oligonucleotide treatment, leading to change in the PK profile. To date, no apparent association of ADA with loss of efficacy or safety findings has been observed.	Assessment of ADAs and monitoring for immunogenicity effects (including hypersensitivity reactions and ADA effect on PK/PD). Guidance on the definition of an anaphylactic reaction and the action plan that needs to be followed with regards to ADA sampling are presented in Appendix G .
Injection Site Reactions	
As with any exogenous substance, injection site reactions may occur as a response to the SC injection of AZD8233. Possible risks associated with SC administration are redness, swelling, pain, induration, and sometimes infection at the administration site. There have been reports in some ASO programs of a few cases of severe ISRs with a high incidence of discomfort to the patient that have led to withdrawal from treatment.
 
In the ongoing clinical programme for AZD8233, mild ISRs have been observed in a few participants (see Section 2.2 for details).
	Monitoring for injection site reactions
Complement Activation	
This is a known class effect of oligonucleotides and appears to be directly plasma concentration (C_{max}) driven. Monkeys are considered more sensitive to complement activation than humans (Crooke ST et al 2016).
 
In the 9-month monkey study, minimal to mild higher complement Bb was observed at ≥ 6 mg/kg/occasion at the end of the
	Assessment of complement activation around C_{max} ($C3a$ [Part A only], $C5a$, Bb)

Potential risk of clinical significance	Rationale for risk	Mitigation Strategy
	study and correlated microscopically with mononuclear cell (predominantly lymphocytic) infiltration/inflammation observed in multiple tissues, including the administration site.	

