7 APPENDIX

7.1 Schedule of Activities

	Screening		Treatment Period							EDV	Follow-up period ^a	Final Follow-up Visit ^a
Visit Number	1	2	3	4	5	6	7	8	9		10, 11, 12, 13, 14, 15	16
Study Week			0	1	3	4	6	8	10		12, 14, 16, 18, 20, 22	24
Study Day	Days -28 to -10	Days -7 to -4	Day 1	Day 8	Day 22	Day 29	Day 43	Day 57	Day 71		Days 85, 99, 113, 127, 141, 155	Day 169
Visit Window				± 1 day	± 2 days		± 2 days	± 2 days				
Informed consent	X											
Optional informed consent for future genetic research sample	X											
Verify eligibility criteria	X		X ⁱ									
Enrolment	X											
Randomisation			X									
Medical history	X											
Concomitant medication review	X	X	X	X	X	X	X	X	X	X	X	X
Demographics	X											
Height	X											
Body weight ^a	X		X		X		X			X	X	X
BMI	X									X		X

	Screening		Treatment Period							EDV	Follow-up period ^a	Final Follow-up Visit ^a
Visit Number	1	2	3	4	5	6	7	8	9		10, 11, 12, 13, 14, 15	16
Study Week			0	1	3	4	6	8	10		12, 14, 16, 18, 20, 22	24
Study Day	Days -28 to -10	Days -7 to -4	Day 1	Day 8	Day 22	Day 29	Day 43	Day 57	Day 71		Days 85, 99, 113, 127, 141, 155	Day 169
Visit Window				± 1 day	± 2 days		± 2 days	± 2 days				
HbA1c	X											
Alcohol and smoking history	X	X										
Viral serology	X											
Pregnancy test (females only)	X ^k		X ^l									
Pregnancy and reproductive status (females only ^m)	X											
IMP administration (AZD8233/Placebo)			X			X		X				
Safety Assessments												
Adverse event review	X (SAEs Only)	X (SAEs Only)	X	X	X	X	X	X	X	X	X	X
Injection site reactions ^b			X	X	X	X	X	X	X	X	X	X
Physical examination (complete)	X		X							X		X
Physical examination (abbreviated)				X	X	X	X	X	X		X	

	Screening		Treatment Period							EDV	Follow-up period ^a	Final Follow-up Visit ^a
Visit Number	1	2	3	4	5	6	7	8	9		10, 11, 12, 13, 14, 15	16
Study Week			0	1	3	4	6	8	10		12, 14, 16, 18, 20, 22	24
Study Day	Days -28 to -10	Days -7 to -4	Day 1	Day 8	Day 22	Day 29	Day 43	Day 57	Day 71		Days 85, 99, 113, 127, 141, 155	Day 169
Visit Window				± 1 day	± 2 days		± 2 days	± 2 days				
Vital signs (blood pressure, pulse and temperature) ^c	X		X	X	X	X	X	X	X	X	X	X
12-lead ECG ^c	X		X	X		X		X		X	X ^j	X
Serum chemistry	X		X	X	X	X	X	X	X	X	X	X
Hematology	X		X	X	X	X	X	X	X	X	X	X
Coagulation parameters	X		X	X	X	X	X	X	X	X	X	X
hs-CRP	X		X					X		X	X	X
Complement activation panel ^d			X			X		X				
Urinalysis	X		X	X	X	X	X	X	X	X	X	X
Urine renal safety biomarkers	X		X	X	X	X	X	X	X	X	X	X
Pharmacodynamics												

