LDL-C ^e		X	X	X	X	X	X	X	X	X	X	X
PCSK9 ^e		X	X	X	X	X	X	X	X	X	X	X

	Screening		Treatment Period							EDV	Follow-up period ^a	Final Follow-up Visit ^a
Visit Number	1	2	3	4	5	6	7	8	9		10, 11, 12, 13, 14, 15	16
Study Week			0	1	3	4	6	8	10		12, 14, 16, 18, 20, 22	24
Study Day	Days -28 to -10	Days -7 to -4	Day 1	Day 8	Day 22	Day 29	Day 43	Day 57	Day 71		Days 85, 99, 113, 127, 141, 155	Day 169
Visit Window				± 1 day	± 2 days		± 2 days	± 2 days				
Triglycerides ^e		X	X	X	X	X	X	X	X	X	X	X
Other lipid parameters ^e			X	X	X	X	X	X	X	X	X	X
Pharmacokinetics												
Plasma sample for total full length ASOs of AZD8233 ^f				X		X	X	X	X	X	X ^f	X
Immunogenicity												
Samples for anti-AZD8233 antibodies ^g			X	X		X		X		X	X ^g	X
Exploratory biomarker analysis												
Biomarker analyses (plasma) ^e	X		X	X	X	X	X	X	X	X	X	X
Biomarker analyses (urine) ^e			X	X	X	X	X	X	X	X	X	X
Genomics Initiative optional, exploratory genetic sample ^h			X									

ADA = antidrug antibody; BMI = body mass index; D = day; ECG = electrocardiogram; EDV = early discontinuation visit; FSH = follicle-stimulating hormone; HbA1c = haemoglobin A1c; hs-CRP = high sensitive C-reactive protein; LDL-C = low-density lipoprotein cholesterol; LH = luteinizing hormone; PCSK9 = proprotein convertase subtilisin/kexin type-9; PK = pharmacokinetic; IMP = Investigational medicinal product

Subjects are required to be fasted for at least 10 hours overnight prior to all study visits except for Visit 1; subjects are permitted to drink water during this period of fasting until 1 hour before blood sampling. On days when subjects attend the clinic in a fasting state, blood and urine samples should be obtained prior to administration of the IMP.

Samples to be obtained from all treatment arms unless specified in the table.

- ^a Weight should be measured in light indoor clothes, without shoes, after using the bathroom. Otherwise, follow the local standard procedure.
- ^b Injection Site Reaction assessments to be collected based on adverse event collection criteria.
- ^c Vital signs and ECG to be measured pre-dose on dosing days.
- ^d Blood samples for complement activation panel will be taken around C_{max} and are to be collected pre-dose and 2 hours (± 5 minutes) post-dose.
- ^e Samples to be obtained pre-dose on dosing days.

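### In the Part B SAP, the Table 1 footnote misstates complement and hs-CRP collection, and the tie rule leaves the pre-dose complement values at Visits 6 and 8 out of the by-visit tables

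*SAP*

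**What the plan says.** Table 1 of Part B SAP 3.3.2 sets the analysis windows for lipids, laboratory parameters and vital signs. An asterisk on the laboratory parameters leads to a footnote with two statements: "Complement activation panel is collected pre-dose on Visits 12, 3, 6 and 8 only" and "Hs-CRP is collected at Visit 1, 8 and all follow-up visits".

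The schedules differ from this. Footnote d of protocol Table 2 (section 1.3) says complement samples "are to be collected pre-dose and 2 hours (± 5 minutes) post-dose", and footnote d in SAP Appendix 7.1 says the same. Both schedules mark complement at Visits 3, 6 and 8, and hs-CRP at Visits 1, 3 and 8, the EDV, the follow-up visits and the final visit.

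For two values in one window, SAP 3.3.2 summarises the one nearest the scheduled day, "or the later value if the values are equidistant from the nominal visit date". The rest become unscheduled visits, and SAP 3.3.3 keeps unscheduled values out of the by-visit tables. Section 4.3.5.2, which covers complement, plans summaries of values and change from baseline by treatment group and visit. It does not mention time relative to dose.

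**The concern.** The footnote disagrees with both schedules on the visit list, on the post-dose draw and on hs-CRP at Visit 3. A programmer or table reader who relies on it has a wrong picture of the data.

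The complement part matters more. Of complement activation, the protocol's risk table (section 2.3.1) says "This is a known class effect of oligonucleotides and appears to be directly plasma concentration", naming Cmax as the driver, and the planned mitigation is sampling around Cmax. The pre-dose and 2-hour draws are therefore a designed pair: the first shows where the marker stands before a dose, and the second shows the response to that dose. If only one of the pair is tabulated, and the footnote labels it as the other, an acute post-dose value can be read as a pre-dose level.

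**Working it through.** No sample size or power figure is involved. The check compares the texts and then follows the SAP's rules.

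**Step 1: footnote against schedules.**

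| Item | SAP Table 1 footnote | Protocol Table 2 and SAP Appendix 7.1 |
|---|---|---|
| Complement visits | 12, 3, 6, 8 | 3, 6, 8 |
| Complement timing | Pre-dose; 2 h not mentioned | Pre-dose and 2 h post-dose |
| Complement draws per completer | 4 | 3 x 2 = 6 |
| hs-CRP visits | 1, 8, follow-up | 1, 3, 8, EDV, follow-up, final |
| hs-CRP draws per completer, EDV aside | 1 + 1 + 7 = 9 | 1 + 1 + 1 + 7 = 10 |

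The 7 are Visits 10 to 16. No dose is given at Visit 12 (Day 113), so a pre-dose sample there has no meaning. If the 12 is a typing or text-extraction slip for 1, 2, it still does not match.

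**Step 2: what the SAP rules do with the scheduled values.**

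- *hs-CRP, Day 1.* Baseline is the last measurement before first dose (SAP 3.3.1.1), and Table 1 adds "Pre-dose values on Day 1 qualify as baseline measurements". The Visit 3 value is the baseline.
- *Complement, Day 1.* The pre-dose value is the baseline. The 2-hour value goes to the Day 1 row, which takes measurements made after the first dose (Table 1, footnote b). Both are kept.
- *Complement, Visits 6 and 8.* Windows work on the actual date. The two samples share a date, so they are equally far from Day 29 (or Day 57). The tie goes to the later one, the 2-hour sample. The pre-dose sample becomes unscheduled and leaves the by-visit table.

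**Step 3: count.** Two visits (6 and 8) x 60 planned participants = 120 pre-dose values displaced, before dropout. With the 10% dropout in protocol 9.2, as a rough guide, 60 x 0.9 = 54 and 54 x 2 = 108.

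**Step 4: what the tables then show.** For Week 8 (Week 4 is the same):

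2 h at Week 8 − pre-dose Day 1 = (pre-dose Week 8 − pre-dose Day 1) + (2 h Week 8 − pre-dose Week 8)

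The by-visit table gives only the left side. The first term on the right is any shift built up over repeated dosing, and the second is the response to that dose. Without the pre-dose Week 8 value the two cannot be separated. On Day 1 there is no such problem, because the pre-dose value is itself the baseline.

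**The case against.** A reader might infer from the footnote that the 2-hour samples near Cmax drop out of the tables, or that the hs-CRP baseline falls back to screening. The documents do not support this. The footnote describes collection and does not tell anyone to select or exclude values. For data collection the SAP refers to the protocol and eCRF, and its own appendix has the right schedule. In the footnote the word 'only' most naturally limits the visits, so reading it as pre-dose samples alone is an inference from its silence about the 2-hour draw. As Step 2 shows, the baseline, Day 1 and tie rules keep exactly the values that this reading would lose.

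It can also be said that the displacement of the pre-dose values is already covered. SAP 3.3 provides for summaries by time point where appropriate, 4.3.5.1 derives change from baseline at every post-baseline time point, and the windows are meant to be exhaustive. This has some force: a careful programmer might split the table unprompted. It does not settle the matter. Section 4.3.5.2 is the specific text for these parameters; it plans tables by visit and cites 3.3.1, not the general line in 3.3. For PK concentrations, section 4.2.5.4 asks for both analysis visit and scheduled time, so the SAP states a time split when it wants one. The tie rule is also explicit about what happens to the value not chosen.

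**Conclusion.** The footnote is wrong on three counts: the complement visits, the complement timing, and the hs-CRP visits. The one-value-per-window rule also removes the scheduled pre-dose complement values at Visits 6 and 8 from the by-visit tables, up to 120 in 60 participants. The Week 4 and Week 8 rows then hold 2-hour values under a footnote that calls the panel pre-dose, and the change from before to after those doses cannot be read.

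This assumes that all 60 participants attend both visits and give both samples, that the recorded sampling time decides which same-day value is later, and that the tables follow 4.3.5.2 as written.

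The effect is limited to safety tables. No sample goes uncollected because of it, listings and any overall minimum or maximum summaries still hold every value, and the LDL-C analysis is untouched. It is a modest point, worth correcting because the fix is nearly free.

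**What to change.** Replace the footnote with wording that matches Appendix 7.1, for example: *Complement (Bb, C5a): pre-dose and 2 h post-dose at Visits 3, 6 and 8. hs-CRP: Visits 1, 3 and 8, EDV, all follow-up visits and the final visit.*

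In SAP 4.3.5.2, state that complement is tabulated by nominal time (pre-dose, 2 h) within Visits 3, 6 and 8, with change from the Day 1 pre-dose value. In 3.3.2, exempt complement from the one-value-per-window rule so that neither scheduled sample is classed as unscheduled.

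The cost is a few lines of SAP text and one extra split in a safety table, using samples already scheduled.

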Final follow-up visit: The final follow-up visit will be performed on Day 169 (± 2 days). PK and ADA sampling is to be performed. A complete physical examination must be performed at the visit, and body weight, BMI, vital signs, and ECG are to be checked. Blood and urine sampling is to be obtained.

The maximum blood volume to be drawn from each participant will not exceed 650 mL over the duration of the study period. Repeat or unscheduled samples may be taken for safety reasons or for technical issues with the samples.

Include the maximum amount of blood collected from each participant over the duration of the study and if any repeat or unscheduled samples may be taken, as appropriate.

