Baseline ^a	Day -28 to Day 1	≤ Day 1
Treatment period		
Visit 2 (Days 1 to 3)	Days 1 to 3	Day 1 ^b – Day 3
Visit 3 (Day 8)	Day 8	Day 4 – Day 18
Visit 6 (Day 29)	Day 29	Day 19 – Day 42
Visit 9 (Day 57 to 59)	Day 57 to Day 59	Day 43 – Day 63
Follow-up period		
Visit 10 (FUP Week 2)	Day 71	Day 64 – Day 77
Visit 11 (FUP Week 4)	Day 85	Day 78 – Day 91
Visit 12 (FUP Week 6)	Day 99	Day 92 – Day 105
Visit 13 (FUP Week 8)	Day 113	Day 106 – Day 119
Visit 14 (FUP Week 10)	Day 127	Day 120 – Day 133
Visit 15 (FUP Week 12)	Day 141	Day 134 – Day 147
Visit 16 (FUP Week 14)	Day 155	Day 148 – Day 161
Visit 17 (FUP Week 16)	Day 169	Day 162 onwards.

^a Baseline is defined as the last measurement prior to first dose of study treatment. Pre-dose values on Day 1 qualify as baseline measurements.

^b Day 1 is defined as date of first dose of study treatment.

Table 3: Analysis visit window for laboratory results and anti-AZD8233 antibodies

Analysis Visits	Scheduled visit day	Analysis visit window (days)
Baseline ^a	Day -28 to Day 1	≤ Day 1
Treatment period		
Visit 2 (Days 1 to 3) ^c	Days 1 to 3	Day 1 ^b – Day 3
Visit 3 (Day 8)	Day 8	Day 4 – Day 18
Visit 6 (Day 29)	Day 29	Day 19 – Day 42
Visit 9 (Day 57 to 59) ^c	Day 57 to Day 59	Day 43 – Day 63
Follow-up period ^d		
Visit 10 (FUP Week 2) ^e	Day 71	Day 64 – Day 77
Visit 11 (FUP Week 4)	Day 85	Day 78 – Day 98
Visit 13 (FUP Week 8)	Day 113	Day 99 – Day 126
Visit 15 (FUP Week 12)	Day 141	Day 127 – Day 154
Visit 17 (FUP Week 16) ^e	Day 169	Day 155 onwards.

^a Baseline is defined as the last measurement prior to first dose of study treatment. Pre-dose values on Day 1 qualify as baseline measurements.

^b Day 1 is defined as date of first dose of study treatment.

^c Complement activation panels are only collected at these time points.

^d Renal safety biomarkers and dipstick urinalysis for hematuria are not collected during follow-up period.

^e Anti-AZD8233 antibodies are collected only at these time points.

Table 4: Analysis visit windows for platelet counts

Analysis Visits	Scheduled visit day	Analysis visit window (days)
Baseline ^a	Day -28 to Day 1	≤ Day 1
Treatment period		
Visit 2 (Days 1 to 3)	Days 1 to 3	Day 1 ^b – Day 3
Visit 3 (Day 8)	Day 8	Day 4 – Day 14
Visit 5 (Day 22)	Day 22	Day 15 – Day 25
Visit 6 (Day 29)	Day 29	Day 26 - Day 36
Visit 8 (Day 44)	Day 44	Day 37 – Day 49
Visit 9 (Day 56)	Day 56	Day 50 - Day 63
Follow-up period		
Visit 10 (FUP Week 2)	Day 71	Day 64 – Day 77
Visit 11 (FUP Week 4)	Day 85	Day 78 – Day 91

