4.3.7 Electrocardiogram

4.3.7.1 Definitions and Derivations

The following parameters or time intervals will be recorded for each ECG: RR, PR interval, QRS duration, QT interval, QTcF interval, and ECG mean heart rate (HR).

From the ECG data, the following parameters will be derived:

- QTcF will be calculated as $QTcF = QT \times RR^{-1/3}$, where the QT interval is in milliseconds and the RR interval is in seconds.
- Heart rate will be calculated, based on the RR interval as $HR = 60 / RR$ interval, where the RR interval is in seconds.

Calculation of derived parameters will be performed after averaging of QT and RR data.

The Investigator will judge whether the overall interpretation is ‘normal’ or ‘abnormal’.

ECG results will be assigned to analysis visits as described in Section 3.3.2.

Change from baseline for ECG parameters (where applicable) will be calculated for all post-baseline visits as the respective visit value minus the baseline value.

Outlier categories with respect to QTcF will be defined as follows:

- Absolute value > 450 ms and ≤ 480 ms
- Absolute value > 480 ms and ≤ 500 ms
- Absolute value > 500 ms
- Increase from baseline > 30 ms and ≤ 60 ms
- Increase from baseline > 60 ms

Missing data will not be imputed and only observed values will be reported in the summary tables and listings. Treatment discontinuation visit will be mapped according to Section 3.3.2.

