- ^f PK sampling to be performed at Visits 4 (Day 8), 6 (Day 29), 7 (Day 43), 8 (Day 57), 9 (Day 71), 10 (Day 85), 12 (Day 113), 14 (Day 141), and final follow-up visit/EDV. Schedule of sampling for Visit 6 (Day 29), 8 (Day 57) is shown below.
Visit 6 (Day 29): pre-dose, Visit 8 (Day 57): pre-dose.
- ^g ADA sampling to be performed at Visits 3 (D 1), 4 (D 8), 6 (D 29), 8 (D 57), 10 (D 85), 12 (D 113), 14 (D 141), and final follow-up visit/EDV. ADA samples to be collected pre-dose on all dosing days.
- ^h If, for any reason, the sample is not drawn pre-dose on Visit 3 (Day 1), it may be taken at any visit until the final follow-up/EDV visit.
- ⁱ Check screening labs and inclusion/exclusion criteria.
- ^j ECG to be performed during the follow-up period at Visits 10 (Day 85), 11 (Day 99), 13 (Day 127), and 15 (Day 155).
- ^k Pregnancy test: Serum β -human chorionic gonadotropin (β -hCG) will be performed on all the women participants, irrespective of childbearing potential.
- ^l Pregnancy test (Day 1): Urine pregnancy test using dipstick will be performed before randomization on all the women participants, irrespective of childbearing potential, at a local laboratory.
- ^m All the women participants should have FSH and LH levels determined, irrespective of childbearing potential.
- ⁿ In the case of early discontinuation, follow-up visit will be performed every 2 weeks after last dose.

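### Part B SAP: the ECG window table has no Week 24 row, so the scheduled Day 169 ECG is left out of the by-visit summary or reported as Week 22

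*SAP*

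**What the plan says.** Protocol section 8, Part B, fixes the last visit: "The final follow-up visit will be performed on Day 169 (± 2 days"). At that visit, "body weight, BMI, vital signs, and ECG are to be checked". The ECG row of the schedule of activities (protocol Table 2; Part B SAP 7.1) carries its own mark in the final follow-up column.

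The follow-up column is qualified by footnote j: "ECG to be performed during the follow-up period at Visits 10 (Day 85), 11 (Day 99), 13 (Day 127), and 15 (Day 155"). The footnote does not apply to the final-visit column.

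Part B SAP 4.3.7.1 states: "ECG results will be assigned to analysis visits as described in Section 3.3.2". Section 4.3.7.2 then summarises ECG values and changes from baseline by treatment group and visit. Section 3.3.2 gives the construction rule: "Analysis visit windows will be constructed such that the upper limit of the window intervals fall halfway between two scheduled visits". Where the gap is odd, the extra day goes to the later visit.

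The follow-up rows of Part B Table 2 (ECG) are Days 85, 99, 127 and 155. The last reads "Day 141 onwards", and there is no Day 169 row. When several values share a window, the one closest to the nominal day is summarised and "the remaining visits will be treated as" unscheduled. Section 3.3.3 keeps unscheduled values out of by-visit tables but in overall summaries and listings.

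**The concern.** A visit that the protocol schedules for ECG has no place in the table that decides which ECGs are summarised by visit. The rows of Table 2 coincide with the days in footnote j, so the table may have been built from the footnote without the separate final-visit mark.

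It does not look like a declared choice. Part B SAP section 2 lists three departures from the protocol's analyses, and dropping the last ECG time point is not one of them. Protocol 9.4.3 promises ECG summaries by treatment group and visit.

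At stake is the last planned ECG, 16 weeks after the last dose. It would be missing from the by-visit safety table for most participants, and under a Week 22 label for those who missed Day 155.

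**Working it through.** **Inputs.** Post-baseline ECG days in Part B: 8, 29, 57, 85, 99, 127, 155 and 169 (schedule of activities, footnote j, and the final-visit column). Protocol windows: Day 155 ± 2 and Day 169 ± 2 (protocol section 8). Last dose: Day 57.

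**Step 1: reproduce Table 2.** Apply the halfway rule to the listed days without Day 169. Day 1 has its own row, so the first window starts on Day 2. A midpoint that falls on a whole day goes to the later visit.

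| Visit | Nominal day | Midpoint to next | Window by rule | Table 2 |
|---|---|---|---|---|
| Week 1 | 8 | (8+29)/2 = 18.5 | 2–18 | 2–18 |
| Week 4 | 29 | (29+57)/2 = 43 | 19–42 | 19–42 |
| Week 8 | 57 | (57+85)/2 = 71 | 43–70 | 43–70 |
| Week 12 | 85 | (85+99)/2 = 92 | 71–91 | 71–91 |
| Week 14 | 99 | (99+127)/2 = 113 | 92–112 | 92–112 |
| Week 18 | 127 | (127+155)/2 = 141 | 113–140 | 113–140 |
| Week 22 | 155 | none listed | 141 onwards | 141 onwards |

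Every row reproduces. The table is what the rule gives when Day 169 is left off the list.

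**Step 2: add Day 169.** (155 + 169)/2 = 162. Week 22 becomes Day 141–161 and Week 24 becomes Day 162 onwards. No other row changes.

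**Step 3: apply the selection rule to Table 2 as written.**
- In-window final ECG: Days 167–171, which is 167 − 155 = 12 to 171 − 155 = 16 days from Day 155.
- In-window Week 22 ECG: Days 153–157, which is 0 to 2 days from Day 155.
- Both present: 5 × 5 = 25 day combinations. The final ECG loses in all 25, because at least 12 exceeds at most 2. Any ECG on Days 144–166 would also displace it, being at most 11 days away.
- Day 155 ECG absent and no nearer ECG in the window: the final ECG is reported as Week 22 on all 5 possible days.

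With the Step 2 windows, both ECGs keep their own row in all 25 combinations.

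**Step 4: size.**
- Week 22 as written, to the end of the final-visit window: 171 − 141 + 1 = 31 days. Under the rule: 161 − 141 + 1 = 21 days.
- Time since last dose: (155 − 57)/7 = 14 weeks and (169 − 57)/7 = 16 weeks.
- Ceiling on ECGs without their own row: about 60 randomised, 60/3 = 20 per arm.

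**Step 5: compare with the other tables.** The three SAPs hold 4 + 3 + 4 = 11 analysis-window tables. Ten have a Day 169 row. Part B Table 1 cuts at 161/162, and the ECG tables of Parts A and C have "Visit 17 (FUP Week 16") from Day 162 onwards. Only Part B Table 2 lacks the row.

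**The case against.** The strongest reply concerns importance. Part B ECG is a descriptive safety summary with no test attached. A reader might infer that the Day 169 ECGs are lost to the analysis, but the documents do not support that. Unscheduled values stay in listings and overall summaries under 3.3.3. Under 3.3.2, subject-level maxima use all values whether or not they appear in a by-visit table. The on-treatment period in 3.3.1.3 runs to the end of study, and the QTcF outlier tabulation is not stated to be by visit. Day 169 is also 112 days after the last dose, or 112/21 = 5.3 to 112/14 = 8 of the 2-to-3-week half-lives given in protocol 4.2. All of this stands and keeps the point minor.

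A reader might also take 60 as the expected number affected. It is only a ceiling. Early discontinuers are followed every two weeks from their last dose, so nominal Day 169 need not apply to them. Section 3.3.2 announces an additional window for them, which is not visible in the text available here. Likewise, the Week 22 row mixes 14-week and 16-week ECGs only when a participant has no ECG nearer Day 155, and the documents give no frequency for that.

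Finally, it is tempting to read 3.3.2 (exhaustive windows) and 3.3.3 (visits outside protocol windows are unscheduled) as a wider contradiction that needs all three SAPs rewritten. The documents do not support that as a defect. The Part B derivations for LDL-C, PCSK9, laboratory values and ECG assign values by 3.3.2, and all three SAPs map discontinuation visits by it too, so a working rule exists. Whether any record would be affected is unknown. Tidier wording there is optional and separate from this point.

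None of these replies touches the missing row itself.

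**Conclusion.** The point holds as a minor correction. Part B Table 2 omits a scheduled ECG visit, contrary to the SAP's own halfway rule and unlike the other ten window tables. For a participant with both ECGs in window, the final one never reaches the by-visit summary. For one without a Day 155 ECG or any nearer value, it appears under the wrong week.

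The effect is confined to Part B descriptive by-visit ECG outputs. The Week 12 LDL-C analysis is unaffected, and no ECG value leaves the listings or overall summaries.

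This assumes that the outputs were, or will be, programmed as Table 2 is written, which the documents do not show. It also assumes participants on the full schedule. Early discontinuers depend on the additional window that 3.3.2 announces.

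**What to change.** In Part B SAP 3.3.2, Table 2, change Week 22 (Day 155) to Day 141–161 and add Week 24 (Day 169), Day 162 onwards. Record the change in the amendment history. Date it relative to database lock and to the unblinding of sponsor personnel at the Week 12 interim (Part B SAP 3.1 and section 5), so that a reader can see what was known when it was made.

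The cost is one edited bound and one new row, with no new data. First check what was programmed. If the code follows the present table, re-run the Part B by-visit ECG outputs; if it already separates Day 169, only the text changes.
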